3.1.2 Secondary

Secondary objectives include assessment of other measures of the effects of oxytocin compared with placebo on reduction of alcohol use as well as effects on alcohol craving, alcohol-related consequences, cigarette smoking and other nicotine use, psychological assessments, retention in the study, and safety and tolerability throughout the study.

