3.2 Study Design

This study is a double-blind, randomized, placebo-controlled, parallel group, multi-site clinical trial designed to assess the efficacy of oxytocin compared with placebo to reduce drinking in 100 subjects (50 in each group) who report 4 or more Diagnostic and Statistical Manual of Mental Disorders – Fifth Edition (DSM-5TM) symptoms of AUD. This study will be conducted at 4 clinical sites. If eligible for the study, subjects will be randomized using a stratified permuted block randomization procedure with "clinical site" as a stratification variable in an approximate 1:1 ratio (targeting 50 subjects per group) to receive either intranasal oxytocin or placebo for 12 weeks.

[figure not shown]
If eligible for the study, subjects will receive blinded intranasal oxytocin at 35 IU once per day or intranasal placebo (same volume once per day) for 2 weeks (initial tolerability assessment period), then for the next 10 weeks (maintenance period) subjects will receive oxytocin at 35 IU/twice per day (BID, totally daily dose 70 IU) or intranasal placebo (same volume twice per day)

Subjects will be seen in the clinic at screening visit(s), at randomization, and at Weeks 2, 3, 4, 6, 8, 10, and 13. During the alternate weeks when subjects will not be coming into the clinic (Weeks 5, 7, 9, 11, and 12), subjects will be contacted once during that week by telephone to encourage study drug compliance and to assess withdrawal, adverse events (AEs), and concomitant medication use. A final follow-up telephone interview will occur during Weeks 14/15 (1-to-2 weeks after the end of dosing).

Enrollment will be halted if 2 or more at least possibly related SAEs as judged by the investigator or medical monitor occur. If this occurs, a DSMB meeting will be convened and a decision, in conjunction with the study Sponsor, will be made regarding stopping the study.

The overall study schema is provided in Figure 1. The study schedule of visits and assessments is shown in Table 1.

Figure 1. Overview of Study Design

*Telephone contact, otherwise visit is in clinic

Oxytocin for Alcohol Use Disorder Protocol Number: NCIG-007R

Table 1. Schedule of Assessments

	Screen						ľ	Mainte	nance					EOS ^a	Safety Follow-up
Study Week	-2 to -1	1	2	3	4	5	6	7	8	9	10	11	12	13	14/15
Clinic Visit #	1	2	3	4	5		6		7		8			9	
Informed Consent	X														
Alcohol Breathalyzer	X	X	X	X	X		X		X		X			X	
Urine Drug Screen ^b	X	X	X	X	X		X		X		X			X	
Locator Form	X														

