4.0 DEFINITION OF ANALYSIS SETS

The study analysis populations will consist of the following:

Full Analysis (FA) Set: The full set is defined as subjects randomized to participate in the study who took at least one dose of investigational product. The full analysis set will be used to evaluate all efficacy and safety endpoints.

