7.0 SAMPLE SIZE CONSIDERATIONS

With an intake sample of 100 subjects (50 subjects per arm) and 12% attrition, it is projected that the sample size for primary endpoint analyses will be 88 (44 subjects per arm). The alpha level for the primary analyses will be 0.05, two-tailed. An estimate of the effect size (Cohen's d) for the investigational products is 0.60. Equal variances in both groups are assumed. These assumptions lead to a projected power of 0.80.

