9.0 STATISTICAL CONSIDERATIONS

9.1 General Considerations

For descriptive purposes, dichotomous and categorical variables will be presented as number of observations and percentages; continuous variables will be given as means, standard deviations (SD), median, minimum (min) and maximum (max). Statistical tests will be two-tailed at a 0.05 Type I error rate. P-values for the primary and secondary endpoints of < 0.05 will be considered statistically significant. Endpoint data will also be screened for outliers and skewness. Appropriate non-parametric tests will be used to compare treatment groups on continuous baseline characteristics that are not normally distributed. Continuous endpoint data that are not normally distributed will be transformed using either a square root, logarithmic, or inverse transformation, the selection of which is determined by skewness and kurtosis statistics with values closest to zero and normalization of histograms. Cohen's d will be used to calculate the effect size for means. Odds ratios will be provided for all dichotomous outcomes. Descriptive statistics – mean, SD, median, min and max – of all endpoint data will be provided for each assessment point or summarized at each week for drinking endpoints. All data will be presented in listings. All analyses will be performed in the full analysis set.

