Characteristic	(N=xx)	(N=xx)	(N=xxx)	p-value ¹
Employment				0.xxx
Employed	xx (xx.x%)	xx (xx.x%)	xx (xx.x%)	
Unemployed	xx (xx.x%)	xx (xx.x%)	xx (xx.x%)	
Income				0.xxx
\$0-\$15,000	xx (xx.x%)	xx (xx.x%)	xx (xx.x%)	
\$15,001-\$30,000	xx (xx.x%)	xx (xx.x%)	xx (xx.x%)	
\$30,001-\$45,000	xx (xx.x%)	xx (xx.x%)	xx (xx.x%)	
\$45,001-60,000	xx (xx.x%)	xx (xx.x%)	xx (xx.x%)	
\$60,001-75,000	xx (xx.x%)	xx (xx.x%)	xx (xx.x%)	
\$75,001-90,000	xx (xx.x%)	xx (xx.x%)	xx (xx.x%)	
\$90,001-105,000	xx (xx.x%)	xx (xx.x%)	xx (xx.x%)	
\$105,001-120,000	xx (xx.x%)	xx (xx.x%)	xx (xx.x%)	
>\$120,000	xx (xx.x%)	xx (xx.x%)	xx (xx.x%)	
Missing	XX	XX	XX	
Occupation				0.xxx
Corporate Executive or Major Professional	xx (xx.x%)	xx (xx.x%)	xx (xx.x%)	
Business Manager or Minor Professional	xx (xx.x%)	xx (xx.x%)	xx (xx.x%)	
Business Administrator, Small Business				
Owner, or Semi-professional	xx (xx.x%)	xx (xx.x%)	xx (xx.x%)	
Clerical Worker, Sales, or Technician	xx (xx.x%)	xx (xx.x%)	xx (xx.x%)	
Skilled Worker	xx (xx.x%)	xx(xx.x%)	xx (xx.x%)	
Semi-skilled Worker	xx (xx.x%)	xx (xx.x%)	xx (xx.x%)	
Unskilled Worker	xx (xx.x%)	xx (xx.x%)	xx (xx.x%)	
Other Occupation	xx (xx.x%)	xx(xx.x%)	xx (xx.x%)	
Unemployed (not paid for services)	xx (xx.x%)	xx (xx.x%)	xx (xx.x%)	
Never Worked	xx (xx.x%)	xx(xx.x%)	xx (xx.x%)	
Missing/ Not Given	XX	XX	XX	

¹ p-value from chi-square test (c), t-test for continuous data, and Fisher's exact test for binary categories (f)

Table 12: Baseline DSM-5 Disorders

	Placebo	Oxytocin	Total
	(N=xx)	(N=xx)	(N=xxx)
DSM-5 Disorders ¹			
Major Depressive Episode	xx (xx.x%)	xx (xx.x%)	xx (xx.x%)
Major Depressive Disorder	xx (xx.x%)	xx (xx.x%)	xx (xx.x%)
Suicidality	xx (xx.x%)	xx (xx.x%)	xx (xx.x%)
Suicide Behavior Disorder	xx (xx.x%)	xx (xx.x%)	xx (xx.x%)
Manic episode	xx (xx.x%)	xx (xx.x%)	xx (xx.x%)
Hypomanic episode	xx (xx.x%)	xx (xx.x%)	xx (xx.x%)
Bipolar I Disorder	xx (xx.x%)	xx (xx.x%)	xx (xx.x%)
Bipolar II Disorder	xx (xx.x%)	xx (xx.x%)	xx (xx.x%)
Other Specified Bipolar Disorder	xx (xx.x%)	xx (xx.x%)	xx (xx.x%)
Panic Disorder	xx (xx.x%)	xx (xx.x%)	xx (xx.x%)
Agoraphobia	xx (xx.x%)	xx (xx.x%)	xx (xx.x%)
Social Anxiety Disorder (Social Phobia)	xx (xx.x%)	xx (xx.x%)	xx (xx.x%)
Obsessive Compulsive Disorder (Past month)	xx (xx.x%)	xx (xx.x%)	xx (xx.x%)
Posttraumatic Stress Disorder (Past month)	xx (xx.x%)	xx (xx.x%)	xx (xx.x%)
Alcohol Use Disorder	xx (xx.x%)	xx (xx.x%)	xx (xx.x%)
Substance Abuse Disorder (Non-alcohol)	xx (xx.x%)	xx (xx.x%)	xx (xx.x%)

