Table 94: Summary of Subjects with Adverse Events by Severity and Relationship – Placebo

	Number of Subjects (%) (N=x)													
	Mild Moderate Severe Life-threatening All Grades													
SOC	MedDRA PT	R	NR	R + NR										
		xx (xx.x%)												

Notes: Events are counted once per subject at the highest severity grade and closest relationship to the investigational product. R= related to investigational product (possibly, probably, definitely). NR = not related to investigational product (unrelated, unlikely).

Table 95: Number and Percentage of Subjects with Adverse Events by Maximum Severity

MedDRA SOC/		Pla	cebo		Oxytocin			
Preferred Term		(N=xx)				(N=	=xx)	Т
	Mild	Moderate	Severe	Life- threatening	Mild	Moderate	Severe	Life- threatening
- Any Adverse Events - SOC	nn (xx.x%)							
- Overall - Preferred term 1	nn (xx.x%) nn (xx.x%)							
Preferred term 2	nn (xx.x%)							

Multiple occurrences of a specific adverse event for a subject are counted once in the frequency for the adverse event. Likewise, multiple occurrences of adverse events within a specific preferred term for a subject are counted once in the frequency for the preferred term.

Programmer's Notes: Order System Organ Class alphabetically and preferred term alphabetically within System Organ Class.

Table 96: Number and Percentage of Subjects with Adverse Events by Maximum Severity During Weeks 1& 2

Same as Table 95 using only first 2 weeks

Table 97: Number and Percentage of Subjects with Adverse Events by Maximum Severity During Weeks 3-12

Same as Table 95 using only weeks 3-12

Table 98: Number and Percentage of Subjects with Adverse Events Occurring in >= 5%

MedDRA SOC/	Placebo	Oxytocin	
Preferred Term	(N=xx)	(N=xx)	p-value ¹
SOC	nn (xx.x%)	nn (xx.x%)	0.xxx
- Overall -			
Preferred term 1	nn (xx.x%)	nn (xx.x%)	0.xxx
Preferred term 2	nn (xx.x%)	nn (xx.x%)	0.xxx

Multiple occurrences of a specific adverse event for a subject are counted once in the frequency for the adverse event. Likewise, multiple occurrences of adverse events within a specific preferred term for a subject are counted once in the frequency for the preferred term. At least 5% occurring in either arm to be included in the table.

1 Fisher's Exact test

Programmer's Notes: Order System Organ Class alphabetically and preferred term alphabetically within System Organ Class.

Table 99: Number and Percentage of Subjects with Adverse Events Leading to Discontinuation of Study

MedDRA SOC/	Placebo	Oxytocin

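### The only between-arm statistic in the adverse-event tables is a p-value; add the risk difference with its 95% confidence interval

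*SAP*

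**What the plan says.** Safety against placebo is part of the secondary objectives: SAP 3.1.2 lists "retention in the study, and safety and tolerability throughout the study". On the analysis set, SAP 4.0 states: "The full analysis set will be used to evaluate all efficacy and safety endpoints". That set is everyone randomized who took at least one dose, so about 50 per arm.

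SAP 9.6.1 describes adverse events by severity, frequency and relationship within MedDRA groupings. It names no between-arm estimate and no test for them. The tests appear only in the shells of SAP 12.1.4:

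- **Table 89** (any AE, any SAE, any related AE): n (%) by arm, footnoted "p-value from chi-square test".
- **Table 90 and its copies 91–92**: n (%) by arm, with a Fisher p-value on the any-event and system-organ-class rows.
- **Table 98**: n (%) by arm, with a Fisher p-value for each class and each preferred term, under the rule "At least 5% occurring in either arm to be included in the table".
- **Tables 93–97, 99 and 100** (severity, relationship, discontinuation): counts and percentages, no test.
- **Table 103** (abnormal nasal mucosa): n (%) by arm, no between-arm statistic.

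SAP 9.1 sets the general level: "Statistical tests will be two-tailed at a 0.05 Type I error rate". The same section says that odds ratios will accompany every dichotomous outcome. Two other safety shells follow that: Table 101 (CIWA-AR) and Table 114 (SNAQ) each have an odds ratio with a 95% interval. The AE shells do not.

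**The concern.** A p-value beside two percentages says whether a difference was detected. It does not say how large an excess on oxytocin the data leave open. With about 50 per arm and events that are mostly uncommon, the second question matters more for safety.

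Table 98 also tests terms from a frequency at which its test has no chance of reaching 0.05. A reader who sees a column of values above 0.05 may conclude that oxytocin adds no adverse events, when the same counts are compatible with a sizeable excess. The trial has a stated safety comparison with placebo, and the planned output would not let it say what excess risk has been excluded.

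**Working it through.** **Inputs.** Arm size: "With an intake sample of 100 subjects (50 subjects per arm) and 12% attrition" (SAP 7.0). The attrition applies to the primary analysis, so 50 per arm is used here. Level: two-sided 0.05 (SAP 9.1). Display threshold: 5% of 50 = 2.5, so 3 subjects.

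**The plan's own figure.** The documents give no power or detectable difference for adverse events. The one stated power, 0.80 for the primary endpoint, reproduces: Φ(0.60 × √(44/2) − 1.96) = Φ(0.854) = 0.80 (0.795 with the noncentral t).

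**Fisher's exact test, k of 50 on oxytocin against 0 of 50.** With equal arms the two-sided p-value is 2 × C(50,k) / C(100,k). The uncorrected chi-square is shown for comparison.

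| Oxytocin / placebo | Observed rate | Fisher p | Uncorrected chi-square p |
|---|---|---|---|
| 3 / 0 | 6% | 0.242 | 0.079 |
| 4 / 0 | 8% | 0.117 | 0.041 |
| 5 / 0 | 10% | 0.056 | 0.022 |
| 6 / 0 | 12% | 0.027 | 0.012 |

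Terms enter Table 98 at 3 events but cannot reach 0.05 against zero until 6. Against 1, 2 or 3 placebo events, 8, 10 or 11 are needed.

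**Sensitivity to arm size.** Allocation is only approximately 1:1. With 4/48 against 0/52, Fisher gives p = 0.0496. With 5/51 against 0/49 it gives 0.057. The 6-event threshold therefore holds at equal arms and can shift with a two-subject imbalance.

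**Chance of p ≥ 0.05 under assumed true rates.** Fisher's test, 50 per arm, summed over both binomials. The placebo rates are assumptions. For the oxytocin side, protocol Table 2 reports nausea at 20% and 13.0% (4200 and 7280 IU) and palpitations in 2 of 8 (5376 IU). The protocol calls this dose range especially relevant.

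| Placebo | Oxytocin | Miss rate |
|---|---|---|
| 0% | 10% | 62% |
| 5% | 15% | 76% |
| 5% | 20% | 49% |
| 5% | 25% | 25% |
| 10% | 25% | 59% |
| 10% | 30% | 36% |
| 20% | 40% | 48% |
| 30% | 50% | 54% |

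**What an interval would add (Newcombe).** For 5/50 against 0/50, the Wilson limits are 4.3% to 21.4% and 0% to 7.1%.

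- Lower limit: 0.100 − √[(0.100 − 0.0435)² + 0.0713²] = 0.009.
- Upper limit: 0.100 + (0.2136 − 0.100) = 0.214.

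The risk difference is +10 points (0.9 to 21.4), where Fisher gives p = 0.056. For 10 against 5 events, p = 0.26 and the difference is +10 points (−4.3 to 24.2), so an excess of 24 points is not excluded.

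**The case against.** The strongest reply is that nothing in the plan equates a non-significant AE comparison with safety. The sentence in SAP 9.1 that declares p < 0.05 significant names primary and secondary endpoints, and SAP 3.3.4 lists adverse events separately as safety endpoints. Counts and percentages are printed by arm throughout, so the difference is one subtraction away. Severity, relationship and discontinuation are tabulated without tests, and every event is listed. Causality assessment, a DSMB and an SAE-triggered enrollment halt do not depend on these p-values. Low power for adverse events is inherent at this size, and the protocol calls the study a pilot.

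Most of this stands, and it rules out four readings that a reader might infer:

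- **That the AE tables compare arms by p-values alone.** They do not, because percentages are shown too. The accurate statement is that the p-value is the only between-arm statistic.
- **That an event in up to 10% on oxytocin and none on placebo can never reach significance.** This is true of an observed 5/50 under Fisher with equal arms. It is not true of an uncorrected chi-square in Table 89 (p = 0.041 at 4 against 0; with a continuity correction, which the SAP does not mention, 0.126). It is not true of a true 10% rate either, which Fisher detects 38% of the time.
- **That a two- to three-fold excess will usually be missed.** That depends on the placebo rate: power is 64% for 10% against 30%, and 89% for 15% against 45%.
- **That nasal mucosa findings go uncompared.** Table 103 shows them by arm, and protocol 10.27 sends abnormal findings to AE reporting where appropriate.

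The reply does not explain why an estimate with interval is given for CIWA-AR and SNAQ but not for adverse events. SAP 9.1's odds-ratio sentence might be read as meaning efficacy outcomes only, but its wording is not limited that way, and Tables 101 and 114 are safety tables. Percentages by themselves also do not show what excess remains possible.

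**Conclusion.** The point holds as a reporting gap. In Tables 89, 90–92 and 98 the only between-arm statistic is a p-value. That departs from SAP 9.1's statement on odds ratios and from the SAP's own Tables 101 and 114.

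The size, at 50 versus 50: no observed split below 6 against 0 reaches 0.05 in Table 98, and the miss rate is about 76% at assumed true rates of 5% and 15%. These figures rest on Fisher's test, near-equal arms and assumed placebo rates. They do not carry over to an uncorrected chi-square in Table 89.

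It would go too far to say that real harms will be reported as no difference. The documents set no such rule, so the risk is one of misreading. The primary inference, the data collected and subject protection are unaffected. This is a cheap improvement.

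**What to change.** Add the oxytocin-minus-placebo risk difference with a 95% confidence interval (Newcombe or Miettinen–Nurminen, one method named in advance) to Tables 89, 90–92 and 98. Add the same to Table 103, which has n (%) by arm but no between-arm statistic.

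Add to SAP 9.6.1 that non-significance will not be taken as evidence of no difference in adverse events, and that the upper confidence limit will be reported as the excess risk not excluded. If the p-values are kept, note that interval and test can disagree near the boundary, as at 5 against 0, and that the interval is the quantity to interpret.

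The cost is SAP wording and one column in existing shells, with no new data and no design change. The downside is slightly more output and wide intervals, which make the safety statement less favourable.

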## 10.8. Columbia Suicide Severity Rating Scale (C-SSRS)

The C-SSRS is a 4-page form asking questions about suicidal ideation, intensity of ideation, and suicidal behavior developed by Posner and collaborators at the New York State Psychiatric Institute (*Oquendo-2003*). This scale is intended for use by trained administrators. The questions contained in the C-SSRS are suggested probes. Ultimately, the determination of the presence of suicidality depends on clinical judgment. Training is required before administering the C-SSRS through a 30-minute interactive slide presentation followed by a question-answer session through the Columbia University Medical Center. Those completing the training are certified to administer the C-SSRS, and will receive a training certificate. As the MINI will be used to establish subject initial eligibility with respect to suicidality, the "Since Last Visit" version of the C-SSRS will be used at each clinic visit starting at Week 1. At Week 1, this scale will be used to assess current suicidal ideation since the MINI interview. This questionnaire will be

administered by a clinical staff member and subject responses will be recorded electronically and will be both the source and eCRF.

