# 11.4.4. Safety Analyses

AEs will be coded using the most recent version of the Medical Dictionary for Regulatory Activities (MedDRA) and will be grouped by system organ class (SOC) and preferred term (PT) designation. The severity, frequency, and relationship of AEs to investigational product will be presented by SOC and PT groupings. Listings of each individual AE including start date, stop date, severity, relationship, outcome, and duration will be provided. Each AE (based on PT) will be counted once only for a given study subject. If the same AE occurred on multiple occasions, the highest severity will be assumed. Thus, study subjects are not counted multiple times in a given numerator in the calculation of frequencies for a specific AE. C-SSRS reports of suicidality or suicidal ideation will be reported as AEs and analyzed as AEs if the investigator determines after an interview with the subject that the responses are consistent with suicidal ideation or attempt.

Clinical chemistry, urine drug screen results, pregnancy test results, BAC results, and SNAQ scores will be reported as summary statistics for each assessment time point. The percentages of subjects in each group with a SNAQ score ≤14 at each visit will be presented. Vital signs will be presented as summary statistics and change from baseline. The proportions of ECG results considered clinically significant will also be provided. In addition, change from baseline (shift tables) will also be presented for clinical chemistry data. The numbers and percentages of subjects who had urine tests positive for THC at each time point for all subjects, for subjects who were positive at baseline, and who were negative at baseline (representing new use) will be summarized. The numbers and proportion of subjects who reported CIWA-AR scores ≥ 10 at any time after the start of dosing will be presented. Buss-Perry Aggression scores, SNAQ scores and body weight changes will be presented for each visit and will be compared between groups using repeated measures ANOVA. The numbers and proportions of subjects mild, moderate, severe microsomia or any smell loss (anosmia) compared with screening assessment using the UPSIT will also be presented.

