3.3.4 Safety Endpoints

Safety endpoints will be analyzed over the entire treatment and follow-up period.

- 1. Vital signs
- 2. Physical examination of the nasal mucosa
- 3. Smell testing with the University of Pennsylvania Smell Identification Test (UPSIT)
- 4. Blood chemistries
- 5. Urine drug screen results
- 6. Blood alcohol concentration (BAC) by breathalyzer
- 7. AEs/SAEs
- 8. Electrocardiogram (ECG) results
- 9. Clinical Institute of Withdrawal Alcohol Revised (CIWA-AR) scores
- 10. Frequency of subjects with suicidal ideation at any time during the treatment period Columbia-Suicide Severity Rating Scale (C-SSRS)
- 11. Change in appetite Simplified Nutritional Appetite Questionnaire (SNAQ) scores and percentage of subjects with SNAQ scores ≤14.
- 12. Buss-Perry Aggression scores (BPAQ)

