9.6 Safety Analysis

9.6.1 Adverse Events

AEs will be coded using the most recent version of the Medical Dictionary for Regulatory Activities (MedDRA) and will be grouped by system, organ, and class (SOC) and preferred term (PT) designation. The severity, frequency, and relationship of AEs to investigational product will be presented by SOC and PT groupings. Listings of each individual AE including start date, stop date, severity, relationship to IP, outcome, action taken (including any treatment administered), and duration will be provided.

Every AE will be assessed for whether or not it qualifies as an SAE. All SAEs will be categorized and listed according to the following categories: Congenital Anomaly or Birth Defect; Persistent or Significant Disability/Incapacity; Results in Death; Requires or Prolongs

Hospitalization; Other Medically Important Serious Event; or Life-Threatening. For deaths, the date and cause of death will be collected and listed. For hospitalizations, the dates of admission and release (discharge) will be collected and listed.

Each AE (based on PT) will be counted once only for a given study subject. If the same AE occurred on multiple occasions, the highest severity will be assumed. Thus, study subjects are not counted multiple times in a given numerator in the calculation of frequencies for a specific AE. C-SSRS reports of suicidality or suicidal ideation will be reported as AEs and analyzed as AEs if the investigator determines after an interview with the subject, that the responses are consistent with suicidal ideation or attempt. Tabulation of suicidal ideation by CSSRS will be presented without hypothesis testing; answers to the C-SSRS will be provided in a subject listing.

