9.6.2 Clinical Laboratory and Point of Care Tests

For clinical laboratory data, descriptive statistics will be generated for all tests performed at screening and at each clinic visit. If a laboratory analysis is repeated, the last measurement performed prior to the clinic visit will be used in the summary statistics for that clinic visit. If an unscheduled clinical laboratory visit occurs prior to a scheduled visit that is missed due to dropout, then the unscheduled visit will be used in the summary statistics for the missed scheduled clinical visit. If an unscheduled clinical laboratory visit occurs between two scheduled clinical visits, then the data from the unscheduled visit will only be presented in the listings and not in summary statistics. In addition, at each post-randomization clinic visit descriptive statistics for change from baseline will be generated. Laboratory values will be plotted as mean \pm standard error over time. All laboratory measurements will be presented in the listings.

Number and percentage of positive urine drug tests and pregnancy tests for screening visits and all treatment and follow-up visits will be tabulated. Results of all urine drug tests and pregnancy tests will be presented in the listings. The percentage of subjects with a positive urine drug test at any time post start of treatment will also be presented by test type and treatment group.

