Table 104: Summary of Other Services Used During Treatment Period

	Placebo	Oxytocin
Services	(N=xx)	(N=xx)
Self Help Meetings		
N	XX	XX
Mean	XX.X	XX.X
SD	XXX.XX	XXX.XX
Median	XX	XX
Min-Max	(xx-xx)	(xx-xx)

	Placebo	Oxytocin
Services	(N=xx)	(N=xx)
Have you visited another health professional to get help reducing drinking?		
N	Xx	XX
Yes n (%)	xx (xx)	xx (xx)

Programmer note: categorize type of professional for those categories reaching 5%

Table 105: Summary of ECG Results

	ASP8062	Placebo
Result	(N=xx)	(N=xx)
Screening		
Normal	nn (xx.x%)	nn (xx.x%)
Abnormal, Not Clinically Significant	nn (xx.x%)	nn (xx.x%)
Abnormal, Clinically Significant	nn (xx.x%)	nn (xx.x%)
End of Study		
Normal	nn (xx.x%)	nn (xx.x%)
Abnormal, Not Clinically Significant	nn (xx.x%)	nn (xx.x%)
Abnormal, Clinically Significant	nn (xx.x%)	nn (xx.x%)

Table 106: Summary of Blood Chemistries

		Placebo				Oxytocin						
Test	N	Mean	SD	Med	Min	Max	N	Mean	SD	Med	Min	Max
Test Name (units)												
Screening												
Week 6												
Change from baseline												
Weeks 8, 10, 13												

Programmers note: table will include creatinine, ALT, AST, total bilirubin, creatinine, sodium, and potassium.

Table 107: Summary of Positive Urine Drug Tests, Pregnancy Test or BAC > 0.000 Any Time During the Study

	Number (% Positive)					
Test	Placebo	Oxytocin				
THC	xx (xx%)	xx (xx%)				
Cocaine	xx (xx%)	xx (xx%)				
Opioids	xx (xx%)	xx (xx%)				
Methamphetamine	xx (xx%)	xx (xx%)				
Amphetamine	xx (xx%)	xx (xx%)				
Benzodiazapines	xx (xx%)	xx (xx%)				
Buprenorphine	xx (xx%)	xx (xx%)				
Methadone	xx (xx%)	xx (xx%)				
Oxycodone	xx (xx%)	xx (xx%)				
MDMA	xx (xx%)	xx (xx%)				
Barbiturates	xx (xx%)	xx (xx%)				
Pregnancy	xx (xx%)	xx (xx%)				
BAC > 0.000	xx (xx%)	xx (xx%)				

Table 108: BPAQ – Each Evaluation During Maintenance Period

			0	xytocin			Placebo						
Study Week	N	Mean	SD	Median	Min	Max	N	Mean	SD	Median	Min	Max	
Physical Aggression													
6	XX	XXX	XXX	XXX	XXX	XXX	XXX	XXX	XXX	XXX	XXX	XXX	
8	XX	XXX	XXX	XXX	XXX	XXX	XXX	XXX	XXX	XXX	XXX	XXX	
10	XX	XXX	XXX	XXX	XXX	XXX	XXX	XXX	XXX	XXX	XXX	XXX	
13	XX	XXX	XXX	XXX	XXX	XXX	XXX	XXX	XXX	XXX	XXX	XXX	
Verbal Aggress	ion												

6	XX	XXX										
8	XX	XXX										
10	XX	XXX										
13	XX	XXX										
Hostility												
6	XX	XXX										
8	XX	XXX										
10	XX	XXX										
13	XX	XXX										
Anger												
6	XX	XXX										
8	XX	XXX										
10	XX	XXX										
13	XX	XXX										

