Shell is same style as Table 109

Table 116: Frequency of Subjects with Suicidal Ideation Any Time During the Study

Number of Subjects Re	Number of Subjects Reporting Suicidal Ideation by C-SSRS (%)										
Placebo Oxytocin p-value											
(N=xx)	(N=xx)										
xx (xx.x%)	xx (xx.x%)	0.xxx									

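### The SAP omits the protocol's THC new-use summary, and the shells of Tables 107 and 116 do not match the SAP text on time window and testing

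*SAP*

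**What the plan says.** **Urine drug tests.** Protocol 11.4.4 commits to the number and percentage of THC positives at every time point for three groups: all subjects, those positive at baseline, and those "who were negative at baseline (representing new use) will be summarized". SAP 9.6.2 makes two statements. First: "Number and percentage of positive urine drug tests and pregnancy tests for screening visits and all treatment and follow-up visits will be tabulated". Second, it promises an any-time summary, worded as follows: "positive urine drug test at any time post start of treatment will also be presented by test type and treatment group". The SAP's only summary shell for post-baseline drug screens is Table 107, "Summary of Positive Urine Drug Tests, Pregnancy Test or BAC > 0.000 Any Time During the Study". It has one row per drug, including one for THC, and no p-value column. Baseline THC status by arm is in Table 15.

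**Suicidal ideation.** SAP 3.3.4, like Protocol 8.3, defines the safety endpoint as "Frequency of subjects with suicidal ideation at any time during the treatment period". The shell, Table 116, is titled "Frequency of Subjects with Suicidal Ideation Any Time During the Study" and has a p-value column. SAP 9.6.1 says: "Tabulation of suicidal ideation by CSSRS will be presented without hypothesis testing". On the first C-SSRS, Protocol 10.8 says: "At Week 1, this scale will be used to assess current suicidal ideation since the MINI interview".

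**The concern.** Tables are programmed from shells. Where a shell differs from the text, the shell is likely to decide what is reported.

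For THC, the protocol set out a specific summary because cannabis users may enter the trial, so a positive result during treatment is ambiguous unless baseline status is shown. Without the split, the safety report cannot say whether either arm took up cannabis during the study.

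For suicidal ideation, a subject who reports ideation at the pre-dose Week 1 check, is evaluated and is then randomized could be counted in the only summary table for an endpoint meant to describe the treatment period. An unplanned p-value on a sparse safety outcome invites over-reading in either direction.

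**Working it through.** No figure in the plan bears on this point, so the check is mainly a comparison of texts.

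**1. Is the THC split anywhere in the SAP?** SAP 9.6.2 does not mention baseline status. Table 15 gives baseline THC only. Table 107 has one THC row. Listing 35 gives individual results. None of these is the three-group, by-visit summary of Protocol 11.4.4, and the SAP gives no reason for leaving it out.

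**2. Does it matter for THC in particular?** Protocol 7.3.2, exclusion 2, bars subjects with a screening or baseline positive for the ten other listed drugs, but admits THC positives unless they have moderate or severe marijuana use disorder. THC is therefore the row where baseline positives are expected.

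**3. How much can one row hide?** The documents give no THC rates, so every input here is an assumption. Let *b* be the share THC-positive at baseline (equal in both arms), *c* the share of those who test positive again after treatment starts, and *u* the rate of new use among baseline negatives. The share counted positive is

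b × c + (1 − b) × u.

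Take u = 5% in one arm and 15% in the other, a true ratio of 15/5 = 3.0. At b = 10% and c = 1: 0.10 + 0.90 × 0.05 = 14.5% and 0.10 + 0.90 × 0.15 = 23.5%, a ratio of 1.62.

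| b | c = 1: shares | ratio | c = 0.7: shares | ratio |
|---|---|---|---|---|
| 10% | 14.5% v 23.5% | 1.62 | 11.5% v 20.5% | 1.78 |
| 20% | 24.0% v 32.0% | 1.33 | 18.0% v 26.0% | 1.44 |
| 30% | 33.5% v 40.5% | 1.21 | 24.5% v 31.5% | 1.29 |
| 40% | 43.0% v 49.0% | 1.14 | 31.0% v 37.0% | 1.19 |

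The c = 1 columns also give the result when pre-dose tests are counted, because every baseline positive then counts. The c = 0.7 columns apply a strict post-start window and recover little. The missing split, rather than the window, causes most of the loss.

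**4. Table 107 window.** Urine is tested at screening and again at Week 1 as part of the final eligibility check (Protocol 7.5). The shell title would take in both; the any-time percentage in SAP 9.6.2 would not. The two conflict, and the text is the more specific.

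**5. Table 116 window.** The Week 1 C-SSRS is among the final eligibility assessments (Protocol 7.5) and looks back to the screening MINI (Protocol 10.8). Under Protocol 7.3.2, exclusion 14 and its note, a yes to either of the first two questions leads to a physician's evaluation and documented judgement, not automatic exclusion. A subject with a pre-dose yes can therefore be randomized. SAP 9.6.1 sets no window, and no SAP text removes Week 1 from Table 116.

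**6. Table 116 p-value.** The column contradicts SAP 9.6.1 directly, and no test is named.

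**The case against.** A reader might infer from the title of Table 107 that the plan counts drug-screen positives from before the first dose as on-treatment events. The documents do not support that. SAP 9.6.2 limits the any-time percentage to results after treatment starts. Baseline positives for the ten other drugs are exclusionary, apart from a narrow re-screening route after opioid use for acute pain, and pregnancy is exclusionary too. Neither table is labelled on-treatment. Nor would significance tests on THC positivity show harm: no such test is planned, and any counts would be invented.

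Much of the information also exists elsewhere. Table 15 gives baseline THC by arm, and Listings 30 and 35 give subject-level C-SSRS and urine results. Subjects whose current suicidality risk a study physician confirms are excluded, so few pre-dose positives should reach Table 116. Ideation confirmed by the investigator is analyzed as an AE. AE assessment starts after the first administration (Protocol 10.2.3), and Tables 91 and 92 split AEs into Weeks 1–2 and 3–12.

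This is right about scale, and it disposes of the stronger reading. It does not supply the THC summary the protocol promised, since a listing is not a summary. It does not bring Table 116 into line with its endpoint, because the AE tables cover only investigator-confirmed ideation. It leaves the p-value contradiction untouched.

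**Conclusion.** The point holds as a minor one, in four parts. The SAP omits a THC summary that the protocol requires. Table 116 uses a wider window than its endpoint and can admit a pre-dose assessment. Table 116 carries a p-value that the text rules out. Table 107's title conflicts with SAP 9.6.2 on the urine drug window; this is a mismatch between shell and text, not a settled plan to count pre-dose results.

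The effect is confined to descriptive safety reporting and does not touch the primary or secondary efficacy analyses. The documents do not allow the number of affected subjects to be estimated. The ratios above show the direction and possible extent of dilution under assumed rates, with equal baseline THC shares in the two arms; they are not a forecast.

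**What to change.** - Add one THC table, by visit and arm, for all subjects, baseline-positive subjects and baseline-negative subjects, as Protocol 11.4.4 requires. Extra rows in an any-time table would not meet the by-visit commitment.
- Restrict Table 116 to C-SSRS assessments made after the first dose, retitle it to match SAP 3.3.4, show Week 1 as a separate baseline row, and delete the p-value column.
- Give the urine drug rows of Table 107 the post-start window of SAP 9.6.2. Keep the screening tabulation that 9.6.2 also asks for, and leave the BAC row on the any-clinic-visit rule of SAP 9.6.4.
- Add a sentence to SAP 9.6.1 stating the C-SSRS window and one to 9.6.2 describing the THC split.

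The cost is one new shell, two edited shells and two sentences. All the data are already collected.
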